The purpose of the Statistical Analysis Plan (SAP) is to describe the implementation of the statistical analysis as planned in section 9 in the clinical study protocol version 00 for the clinical trial CAIN457ADE08 (METABOLYX). Additional analyses, specifications or deviations from the study protocol planned before database lock will also be discussed in this SAP.

1.1 Study design

This study is designed as a randomized, open-label, parallel-group, active comparator-controlled trial with two treatment arms. The design is shown in Figure 1-1.

Figure 1-1 Study Design

[figure not shown]

Fig. 1-1: Study Design: R Randomization, * During the extension period the lifestyle intervention can be continued by patients who have been in arm B during the core study or it can be started by patients who have been in arm A. Participation in the lifestyle intervention during the extension period is **not** mandatory. ¶Participation in the extension period itself is mandatory. Psoriasis treatment during the extension period can be chosen freely by the Investigator. No study drug is supplied during the extension period.

Core study: After providing informed consent patients will be screened for eligibility for a period of 1-4 weeks prior to inclusion into the study. If eligible, patients will then be randomized to one of the two treatment arms, which are the following:

- **Arm A:** Patients in arm A receive a regular induction followed by 4-weekly maintenance treatment with Secukinumab 300 mg s.c. until week 28, where they complete the core study. The last Secukinumab injection is performed at week 24.
- **Arm B:** Patients in arm B receive a regular induction followed by 4-weekly maintenance treatment with Secukinumab 300 mg s.c. until week 28. The last Secukinumab injection is performed at week 24. **In addition to Secukinumab treatment patients in arm B participate in a lifestyle intervention program.**

The core study ends at week 28.

Extension period: After 28 weeks the study continues with an extension period, during which lifestyle intervention is offered to all patients, irrespective of their prior treatment arm. This means that patients of arm B, who are willing to, can continue their previously started lifestyle intervention program and patients of arm A, who are willing to, can start the lifestyle intervention program at the beginning of the extension period. **All patients, irrespective of their decision whether to start/ continue lifestyle intervention or not, have to participate in the extension period and visit their dermatologic study center for scheduled visits.** The extension period ends at week 56, where all patients complete the study. There will be no study drug supply during the extension period. The treating physician can choose psoriasis therapy freely according to his discretion.

[figure not shown]
1.2 Study objectives and endpoints

[figure not shown]
The study objectives and endpoints are described in Table 1-1

Table 1-1 Study objectives and endpoints

Objectives	Endpoints
Primary Objective 1. To demonstrate that the combination of Secukinumab (300 mg, 4-weekly s.c.) with lifestyle intervention results in higher psoriasis treatment efficacy than Secukinumab alone in psoriasis patients with concomitant metabolic syndrome	Endpoints for primary objective 1. Percentage of patients achieving PASI90 at week 28 in both randomized treatment arms, Secukinumab alone and Secukinumab combined with lifestyle intervention
Secondary Objectives 1. To explore treatment efficacy of Secukinumab (300 mg, 4-weekly s.c.) combined with lifestyle intervention in comparison to Secukinumab alone 2. To evaluate the effect of Secukinumab (300 mg, 4-weekly s.c.) combined with lifestyle intervention in comparison to Secukinumab alone on systemic inflammation 3. To evaluate the effect of Secukinumab (300 mg, 4-weekly s.c.) combined with lifestyle intervention in comparison to	Endpoints for secondary objectives 1. PASI75, 90 and 100 as well as absolute PASI scores in both treatment arms at week 1, 2, 3, 4, 8, 12, 16, 20, 24 and 28 2. hsCRP in both treatment arms throughout the duration of the core study 3. HbA1c, fructosamine and fasting plasma glucose in both treatment arms throughout the duration of the core study

Objectives	Endpoints
Secukinumab alone on glucose metabolism	
4. To evaluate the effect of Secukinumab (300 mg, 4-weekly s.c.) combined with lifestyle intervention in comparison to Secukinumab alone on lipid metabolism	4. Total cholesterol, LDL, HDL and triglycerides in both treatment arms throughout the duration of the core study
5. To evaluate the effect of Secukinumab (300 mg, 4-weekly s.c.) combined with lifestyle intervention in comparison to Secukinumab alone on body weight and waist circumference	5. Waist circumference (cm), body weight (kg) and BMI (kg/m ²) in both treatment arms throughout the duration of the core study
6. To evaluate the effect of Secukinumab (300 mg, 4-weekly s.c.) combined with lifestyle intervention in comparison to Secukinumab alone on systolic and diastolic blood pressure	6. Systolic and diastolic blood pressure (mmHg) in both treatment arms throughout the duration of the core study
7. To evaluate the effect of Secukinumab (300 mg, 4-weekly s.c.) combined with lifestyle intervention in comparison to Secukinumab alone on health-related quality of life, itch, pain and scaling as well as mental well-being	7. Absolute DLQI, relative change of DLQI, proportion of patients with DLQI 0/1, absolute WHO-5, relative change in WHO-5, absolute self-assessed itch, pain, scaling, relative change in self-assessed itch, pain, scaling in both treatment arms throughout the duration of the core study

Objectives	Endpoints
	
5. To explore the effect of Secukinumab (300 mg, 4-weekly s.c.) combined with lifestyle intervention in comparison to Secukinumab alone on biomarkers including but not limited to those linked to lipid, glucose, muscle and bone metabolism, liver fibrosis/steatosis, heart injury, as well as to inflammatory processes in a subgroup of 100 patients (50 treated with secukinumab and lifestyle intervention and 50 treated with secukinumab alone)	5. At baseline (week 0), week 16 and week 28 the following markers will be assessed: Free fatty acid serum profile, sThy-1, adiponectin, leptin, insulin, HOMA-IR, proinsulin, IL-6, TNF-alpha, M30 assay, IL-1 beta, IL-1Ra, IL-18, IL-18bp, P1NP, CTX, RANKL, OPG, sclerostin, NT-proBNP, CD154, and a 30-panel multiplex inflammatory cytokine and chemokines panel

2 Statistical methods

This section contains information that will be used to draft CSR Section 9.7 on statistical analysis.

2.1 Data analysis general information

All statistical analysis will be performed by Novartis Product Lifecycle Services (PLS). Data will be analyzed by statistical software SAS version 9.4 according to the data analysis section 9 of the study protocol.

2.1.1 General definitions

Summary statistics for continuous variables will include N (the number of subjects in the analysis set), n (the number of subjects with available/imputed value), mean, standard deviation (SD), median, minimum & maximum. Summary statistics for discrete variables will be presented in contingency tables and will include absolute and relative frequencies for non-missing data. A row (category) denoted “Missing” will be included in count tabulations if a non-zero count of missing values is present. Percentages will be calculated using the number of patients in the relevant population or subgroup as the denominator. If a count of zero is obtained, the zero count and percentage will still be displayed.

If not otherwise specified, p-values will be presented as two-sided p-values along with the two sided confidence interval.

Unless otherwise stated, the level of significance will be set to 5% (two-sided).

Change from baseline and percentage change from baseline will only be summarized for subjects with both baseline and post-baseline values and will be calculated wherever applicable as:

Change from baseline = post-baseline value – baseline value.

Percentage change from baseline = ((Change from baseline value) / (baseline value)) * 100

2.1.1.1 Study Treatment and Study Day

The day of randomization visit where the patients were allocated to their respective treatment arm i.e. Arm A or Arm B, respectively is defined as Day 1. All study days will be labelled relative to Day 1. Day 0 will not be used, the day before Day 1 is Day -1.

For events occurring on or after Day 1,

Study day = [Date of event] - [Date of first dose] + 1

For events occurring prior to Day 1,

Study day = [Date of event] - [Date of first dose]

2.1.1.2 Screening, baseline and post-baseline definitions

Screening period refers to the period starting from signing the informed consent until randomization or screening failure. Per protocol, subject informed consent must be obtained prior to performing any study related activity. The date of signing informed consent is the start date of screening period. Any assessment obtained during the screening period will be labeled screening assessment.

For efficacy analyses, baseline is the last available pre-dose assessment obtained at Visit 2. If the measurements at Visit 2 are missing then the measurements obtained at Visit 1 will be considered as the baseline. All assessments obtained after Visit 2, are considered as post-baseline.

For safety analyses, baseline is the last assessment obtained before the first dose of study treatment i.e. Secukinumab, is Visit 2. If the measurements at Visit 2 are missing then the measurement at Visit 1 will be considered as the baseline. All assessments obtained after the first dose of study treatment i.e. Secukinumab, are considered as post-baseline.

2.2 Analysis sets

The following analysis sets will be used for the data analysis.

Enrolled Set (ENR): The ENR will consist of all patients who provided signed and dated informed consent

Randomized Set (RAN): The RAN will consist of all patients who were randomized into this study at baseline. Patients in the RAN will be analyzed according to the treatment they were randomized to.

Safety Set (SAF): The SAF will consist of all patients who received at least one dose of study treatment i.e. Secukinumab. Patients will be analyzed according to the treatment they received, i.e. secukinumab alone or Secukinumab with life-style intervention.

Full Analysis Set (FAS): The FAS will consist of all patients who were randomized into this study at Baseline and received at least one dose of study treatment i.e. Secukinumab. Following the intent-to-treat principle, patients in the FAS will be analyzed according to the treatment assigned at randomization.

2.3 Patient disposition, demographics and other baseline characteristics

2.3.1 Patient disposition

The number of patients screened will be presented along with the reasons for screen failures for all the subjects in the ENR dataset. The number and percentage of patients screened, screen failures, randomized, completed or discontinued from the study (i.e. using baseline disposition CRF and treatment period disposition CRF), including reasons for discontinuation will be presented by treatment group for all patients in the ENR dataset. Patients who screen-failed and

were re-screened under a new patient number will have earlier screening numbers collected on the re-screening CRF. Patients will be counted once in the total number of screenings.

The number and percentage of patients with major protocol deviations (see [Section 5.3](#)) will be tabulated by category and deviation in the RAN dataset. Protocol deviations will be listed with date, study day of occurrence, deviation and severity codes.

Moreover, a patient flow diagram of the ENR population will be presented in accordance with the CONSORT guidelines (<http://www.consort-statement.org/>). Demographics and other baseline characteristics

Descriptive statistics for the background and demographic data will be provided for the FAS dataset. Continuous variables will be summarized using N (the number of subjects in the analysis set), n (the number of subjects with available/imputed value), mean, median, standard deviation, minimum and maximum.

Frequency counts and percentages will be presented for categorical variables for non-missing data. A row (category) denoted “Missing” will be included in count tabulations if a non-zero count of missing values is present. Percentages will be calculated using the number of patients in the relevant population or subgroup as the denominator. If a count of zero is obtained, the zero count and percentage will still be displayed. Two-sided 95% Confidence intervals will be evaluated and reported for frequency percentages using clopper-pearson / Exact method.

2.3.1.1 Demographic and background characteristics

The following data will be summarized:

- age (in years, and year categories ≤ 65 , > 65)
- gender (male/female)
- child bearing status (able to bear children/post-menopausal/sterile - of child bearing age)
- race (Asian/Caucasian/Black or African American/Unknown/Other)
- source of subject referral
- smoking status (never/current/former)
- average pack year (former/current/overall)
- height (cm)
- weight (kg)
- body mass index (BMI) = $\text{weight (kg)} / (\text{height (meters)})^2$
- waist circumference (cm)
- hip circumference (cm)
- waist to hip ratio = $\text{waist circumference (cm)} / \text{hip circumference (cm)}$
- sitting pulse (bpm)
- systolic and diastolic blood pressure (mmHg)
- serum pregnancy test (negative/positive)

2.3.1.2 History of previous psoriasis treatments

The following medical history and prior treatments captured at Visit 1 will also be summarized for the FAS dataset.

1. The occurrence (yes/no/unknown), status at start of study (ongoing - no/yes) and duration (in years) of cardiovascular diseases by medical history term
2. The occurrence (yes/no), status at start of study (active or ongoing - no/yes) and duration (in years) of plaque-type, nail, scalp, palms and soles
3. The occurrence (yes/no), (ongoing – no/yes), type (if ongoing), and duration (in years) of psoriatic arthritis
4. The occurrence of prior psoriasis therapy including name of therapy/medication, type of therapy, type of psoriasis treated, total number of months of exposure and reason for discontinuation.

Duration (in years) of disease is calculated as (Visit 1 date – date of first diagnosis of disease + 1)/365.25.

All prior medications will be summarized by Anatomic Therapeutic Chemical (ATC) class and PT according to the World Health Organization (WHO) Drug Reference List dictionary (version 201909 or higher). The ATC class will be presented in alphabetical order. Preferred terms will be sorted by decreasing proportion and alphabetical order.

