4.1 Inclusion criteria

Patients/subjects eligible for inclusion in this study must fulfill all of the following criteria:

1. Written informed consent must be obtained before any assessment is performed.
2. Men or women of at least 18 years of age at the time of screening.
3. Patients must be able to understand and communicate with the investigator and must be willing and able to comply with all study procedures.
4. Patients with moderate to severe plaque-type psoriasis who are candidates for systemic therapy, diagnosed at least 6 month before randomization and baseline value of
 - PASI > 10 and

- DLQI > 10 and
 - Body Surface Area (BSA) affected by plaque-type psoriasis $\geq 10\%$
5. Fulfillment of Metabolic Syndrome definition (Alberti et al., 2009), which means fulfillment of ≥ 3 of the following criteria **at screening visit**:
- **Fasting** (8 hours) plasma glucose ≥ 100 mg/dl or ongoing antidiabetic drug treatment (defined as: metformin, DPP4 inhibitors, GLP1 analogues, SGLT2 inhibitors)
 - Abdominal obesity defined by elevated waist circumference (measured as defined in section 6.4.5): Male: ≥ 94 cm, female: ≥ 80 cm (except for patients of Asian, South or Central American ethnicity, for whom the cut off values are: Male: ≥ 90 cm, female: ≥ 80 cm)
 - **Fasting** (8 hours) triglycerides ≥ 150 mg/dl or ongoing drug treatment for elevated triglycerides (defined as: fibrates or nicotinic acid).
 - **Fasting** (8 hours) HDL-C < 40 mg/dl in men or < 50 mg/dl in women or ongoing drug treatment for reduced HDL-C (defined as: fibrates, nicotinic acid or statins).
 - **Resting** blood pressure: Systolic blood pressure ≥ 130 and/ or diastolic blood pressure ≥ 85 mmHg (measured as defined in section 6.4.6) or ongoing antihypertensive drug treatment [defined as: ACE inhibitors, beta blockers, angiotensin receptor antagonists (e.g. Valsartan), aldosterone receptor antagonists, diuretics, nitrates, calcium channel blockers (e.g. Verapamil, Nifedipin), Aliskiren, Clonidin, alpha1 receptor antagonists (e.g. Doxazosin), Dihydralazin, Minoxidil, Moxonidin or Methyldopa].
6. Willingness and motivation to actively participate in a lifestyle intervention, which means patients need to be willing to increase physical activity and to change dietary habits.

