5.5.3.2 Handling of additional treatment

Dermatologic study site personnel will instruct patients how to contact their lifestyle intervention trainer in order to participate in the lifestyle intervention program. For patients randomized to receive concomitant lifestyle intervention **it is mandatory to participate in the lifestyle intervention and to show up to the counseling appointments scheduled**. All patient materials which are part of the lifestyle intervention (Lese-/Arbeitsbuch, information flyer, activity tracker, Theraband, scale, tape measure) are given to patients in arm B at randomization visit (study visit 2).

5.5.4 Instructions for prescribing and taking study treatment/ for participating in the lifestyle intervention program

The first study treatment administration will occur at baseline (visit 2) after the inclusion/exclusion criteria have been confirmed and all study scheduled assessments have been performed.

All doses of study treatment are administered at the study site by study site personnel or by the patient himself under the supervision of study site personnel. All study assessments, including blood withdrawal and completion of Patient Reported Outcomes (PROs), i.e. DLQI, should be completed prior to the injection of study treatment. The flow of work and the consecutive steps of assessments including Clinical Outcome Assessments (COA) are given in Section 6.

In single, **exceptional** cases where a visit needs to be skipped e.g. due to business/ working travels of the patient, home administration of study treatment by the patient himself without supervision is allowed at the discretion of the investigator for up to one time per patient between week 8 and week 24. In these cases the investigator is allowed to provide the patient at most one dose of study treatment (2 pre-filled syringes) in advance. Study treatment must be transported in a suitable cooled bag, which will be provided at the study sites. During home administrations subjects are expected to contact the investigator/site staff in case they are experiencing any AE/SAE or have any concerns or are unable for any reason to take the study treatment as prescribed. A visit should be scheduled as close as possible to the time of the per protocol planned visit which had to be skipped. At this visit all assessments of the skipped visit should be performed but no study drug will be administered.

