5.1.3 Other imputations

Medical history date of diagnosis imputation

Completely missing dates and partially missing end dates will not be imputed. Partial dates of diagnosis will be compared to the treatment start date.

- If diagnosis year < study treatment start date year and diagnosis month is missing, the imputed diagnosis date is set to the mid-year point (01JULYYYY)

- Else if diagnosis month is not missing, the imputed diagnosis date is set to the mid-month point (15MONYYYY)
- If diagnosis year = study treatment start date year and (diagnosis month is missing OR diagnosis month is equal to study treatment start month), the imputed diagnosis date is set to one day before study treatment start date

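### A year-only diagnosis date in the first-dose year is imputed to a day after Visit 1, where disease duration ends, so such a record gets a negative duration

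*SAP*

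**What the plan says.** SAP here means the main (core-study) SAP.

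- **Duration.** SAP 2.3.1.2 summarises duration in years for cardiovascular diseases, for plaque-type, nail, scalp, and palms and soles disease, and for psoriatic arthritis. The formula is: "Duration (in years) of disease is calculated as (Visit 1 date – date of first diagnosis of disease + 1)/365.25".
- **Partial diagnosis dates.** SAP 5.1.3 has three bullets. An earlier year with unknown month goes to 1 July. The second bullet reads: "Else if diagnosis month is not missing, the imputed diagnosis date is set to the mid-month point (15MONYYYY"). The third applies under this condition: "If diagnosis year = study treatment start date year and (diagnosis month is missing OR diagnosis month is equal to study treatment start month"). In that case "the imputed diagnosis date is set to one day before study treatment start date".
- **Timing.** SAP 1.1 says "patients will be screened for eligibility for a period of 1-4 weeks prior to inclusion into the study", and Protocol Table 6-1 places Visit 1 on Day -28 to Day -7. Protocol 5.5.4 says "The first study treatment administration will occur at baseline (visit 2"). SAP 2.1.1.1 adds: "Day 0 will not be used, the day before Day 1 is Day -1".
- **Eligibility.** Protocol 4.1, criterion 4, requires plaque psoriasis to have been "diagnosed at least 6 month before randomization".
- **Reporting.** SAP 2.1.1 and 2.3.1 count imputed values in n and report mean, SD, median, minimum and maximum.

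**The concern.** The two rules use different reference dates. Duration stops at Visit 1, while the third imputation bullet is tied to first dose at Visit 2, one to four weeks later. A diagnosis date placed on the day before first dose therefore lies after the date to which duration is counted. Neither section caps the imputed date or says what to do with a negative duration.

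Because imputed values enter the summaries, a single such record would set the minimum of a baseline duration table to an impossible value. For plaque psoriasis the imputed date would also be one that criterion 4 excludes for an eligible patient. Without a written rule, the programming team would have to settle the matter ad hoc.

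**Working it through.** The plan states no figure on this point, so there is nothing to reproduce. The check is date arithmetic on the stated rules.

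**Inputs.** Let D be the date of first dose (Visit 2, Day 1). There is no Day 0, so Visit 1 on Day -k is D - k, with k = 7 to 28 (Table 6-1). The imputed diagnosis date under the third bullet is D - 1.

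**Duration under the third bullet**

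Duration in days = (D - k) - (D - 1) + 1 = 2 - k.

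| Visit 1 | Duration (days) | Years (days / 365.25) |
|---|---|---|
| Day -7 | 2 - 7 = -5 | -0.014 |
| Day -14 | 2 - 14 = -12 | -0.033 |
| Day -28 | 2 - 28 = -26 | -0.071 |

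The result is zero or positive only for k = 1 or 2, which the schedule does not allow. The recommended 2-day tolerance for Visit 2 (Protocol section 6) could shorten k to 5, which still gives -3 days. An enumeration of every first-dose date in a calendar year, every k from 7 to 28 and every possible true diagnosis date on or before Visit 1 gave only negative values in this branch, from -26 to -5 days.

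**Which records reach this branch**

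- Diagnosis in the first-dose year with unknown month: always.
- Diagnosis in the first-dose year with month equal to the first-dose month: this depends on the reading. If the second bullet covers any known month, the date goes to the 15th. If the third bullet overrides it, the date goes to D - 1. The SAP does not say which.
- Diagnosis in the first-dose year with a known earlier month: not this branch. Where the 15th is used, duration is usually positive. It can still be negative when the diagnosis month is the month of Visit 1. The worst case is Visit 1 on the 1st: 1 - 15 + 1 = -13 days.

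**Eligible plaque-psoriasis patients**

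Diagnosis is at least 6 months before randomisation, so the first-dose-month trigger cannot occur. The unknown-month trigger needs diagnosis and first dose in the same calendar year, hence a first dose in about the second half of the year. The true duration at Visit 1 then lies between:

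- lower end: diagnosis 6 months (about 183 days) before first dose, Visit 1 on Day -28: 183 - 28 + 1 = 156 days = 0.43 years;
- upper end: diagnosis 1 January, first dose 31 December, Visit 1 on 24 December: 358 days = 0.98 years.

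**Example.** First dose 15 October, Visit 1 on 1 October, year only recorded. The imputed diagnosis is 14 October and the duration is -12 days = -0.033 years. If the true date was 10 February, the true duration is 234 days = 0.64 years.

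**Effect on the overall mean.** With about 760 patients, one plaque-psoriasis record wrong by 0.5 to 1 year moves the mean by 0.5/760 = 0.0007 to 1/760 = 0.0013 years. Ten such records move it by 0.007 to 0.013 years.

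**The case against.** The strongest reply concerns scope.

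- **Does 5.1.3 apply?** Its heading refers to medical history. SAP 2.3.1.3, on medical history, leaves out psoriasis, psoriatic arthritis and cardiovascular disease, and the protocol collects psoriasis history and cardiovascular history on their own forms. Applying 5.1.3 to these dates is therefore an inference. It is a reasonable one: SAP 2.3.1.2 describes its own content as medical history, and no other rule for partial diagnosis dates exists. It remains an assumption.
- **Are all same-year partial dates affected?** A reader might infer so. The text does not support that, because a known earlier month is not sent to the day before first dose, and the first-dose-month case is ambiguous.
- **Will the tables contain negative values and a lower mean?** A reader might infer this too. The documents give no count, and the number could be zero. The calculation above shows a negligible shift in the overall mean for plaque psoriasis. Smaller psoriatic arthritis or cardiovascular denominators could shift more, but nothing in the documents lets that be sized.
- **Does the clash with criterion 4 affect eligibility?** No section derives eligibility from the imputed date, so it has no such consequence.

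These points narrow the finding. They do not answer the arithmetic: where the third bullet governs and Visit 1 is on schedule, the duration is negative, and no other section corrects it.

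**Conclusion.** The two SAP sections are inconsistent as written. A diagnosis in the first-dose year with unknown month gets a duration of -5 to -26 days whenever Visit 1 is on schedule. The same holds for a month equal to the first-dose month if the third bullet prevails. For an eligible plaque-psoriasis patient the error is about half a year to one year per record.

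This rests on two assumptions: that 5.1.3 governs the diagnosis dates used in 2.3.1.2, and that Visit 1 falls within the scheduled days. The number of records is unknown and probably small. Mainly the reported minimum is at stake. Disease duration is a descriptive baseline item and is not a term in the primary or secondary efficacy models (SAP 2.5.2 and 2.6.1), so no efficacy result changes. This is a minor correction, worth making because a negative disease duration would be visibly wrong.

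**What to change.** Use one reference date in both sections:

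1. In SAP 2.3.1.2 or 5.1.3, state that the diagnosis date used for duration is the earlier of the 5.1.3 imputed date and the Visit 1 date. Apply this to every disease in 2.3.1.2, including nail, scalp, and palms and soles. A capped record then has a duration of 1 day (0.003 years). The cap also removes the negative values that can arise from the 15th-of-month bullet.
2. State which 5.1.3 bullet takes precedence when the diagnosis month equals the first-dose month.
3. Optionally, for year-only plaque-psoriasis dates, also cap at 6 months before randomisation when that date falls in the recorded diagnosis year. In the example this gives 15 April and 170 days = 0.47 years, which agrees with criterion 4.

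The Visit 1 cap corrects the sign but still understates duration for recent diagnoses. Step 3 reduces that for plaque psoriasis. A midpoint rule starting from 1 January is less safe, because its bounds can reverse, for example with Visit 1 in December and first dose in January.

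The cost is one or two sentences in the SAP and a small change to the derivation code. No new data are needed.
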